Reducing elevated pain-related fear promotes participation in daily activities¹⁻⁴. When patients experience how disengagement from safety behaviors does not lead to catastrophic consequences, their misinterpretations are challenged and disconfirmed, enabling them to correct their fear expectancies⁵⁻⁷. **GET Living** is the first program to explicitly targeted pain-related fear and associated disability in adolescents. Currently, most rehabilitative treatments for adolescents with chronic pain involve promoting pain coping strategies via psychology with separate physical therapy prescribed. Unfortunately, the debilitating influence of pain-related fear can stymy progress in both domains resulting in continued high healthcare utilization without symptomatic improvement.

Design and Outcomes

This study will be a randomized control trial (RCT) including approximately 74 children, ages 8-18, with musculoskeletal pain who present for treatment at Stanford Children's Health (SCH).

A “**participant**” in this study is defined as a child and at least one parent. The term “*patient*” is used to describe the child participant only. Participants will attend an initial baseline assessment (BAS) to perform consent/asset, undergo a biomechanical assessment by the Motion and Sports Performance Laboratory of SCH, and complete self-report questionnaires. Child participants will also be given an Actigraph and will be introduced to the daily diaries. Following BAS, participants will undergo a pre-treatment baseline period where daily diaries will be collected and Actigraphy monitoring will occur. After the baseline period, participants will be randomly assigned to a treatment group, Graded Exposure Therapy (GET Living) or Typical Pain Management (TPM) stratified on their fear and disability scores. Participants in the GET Living intervention group (n=37) will engage in 1-hour sessions of GET Living for 12 sessions jointly facilitated by a pain psychology therapist and physical therapist. Participants randomized into the TPM treatment group (n = 37) will engage in 6 sessions of cognitive behavioral therapy and 6 sessions of physical therapy following BAS. Parents enrolled into the TPM arm will engage in 3 parent-only sessions with the child’s cognitive-behavioral therapist. All participants complete a Daily Diary during treatment.

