5. STUDY INTERVENTIONS

5.1 Interventions, Administration, and Duration

GET Living: Participants randomized into the **GET Living** intervention group, will participate in 12 sessions, 1-hour each, delivered twice a week over for up to 6 weeks.

Phase I-III. The goals of Phase I-III are to educate the participants about the fear avoidance model of pain (individual and interpersonal), present the treatment rationale and formulation, create values-based treatment goals to enhance motivation, and create a pain-related fear hierarchy from the PHODA-YE results to design specific exposures. The pain psychology therapist (PSY) and PT are both present for these sessions to ensure that the treatment message is consistent from both providers to the family. Most of these activities are conducted jointly with the adolescent and parent present, although this varies with the developmental level of the adolescent. For example, while younger adolescents require parental input when developing fear hierarchies, most older adolescents do not want or need parent involvement to complete this task. In addition, depending on parent awareness of their own distress and behavior that may be impacting their adolescent's functioning, the interpersonal fear avoidance model formulation may initially be presented separately. The decision on whom to include for the different treatment exercises in these initial sessions will be jointly negotiated by the therapists, patient, and parents.

Phase IV. Graded Exposure consists of engaging in activities perceived as potentially 'harmful' or 'worrisome' in a controlled and continuous manner in order to elicit anxiety and to foster habituation and the subsequent

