Typical Pain Management (TPM) is a treatment intervention that is representative of current standards of care in a multidisciplinary pain clinic setting. We calculated historical PPMC treatment data for patients who met enrollment criteria (Mean sessions: Psychology=5 and PT=4). To ensure dose equivalency, we increased this to 6-Psychology/6-PT with 3 parent-only sessions. The CBT has been adapted from published manual for CBT treatment

of pediatric chronic pain and depressive symptoms ⁵² and the PT sessions are based on Guide to Physical Therapy Practice 3.0⁵¹.

Overview. The protocol consists of approximately 12 sessions, 1-hour each, delivered twice a week, on average for 6 weeks. Patient and parent will complete daily diaries and patients will wear the Actigraph throughout the duration of treatment. Sessions will alternate between psychological CBT sessions and Physical Therapy sessions, as outlined in Table 2 below. 3 Parent-only CBT sessions with the pain psychologist will be included to address parental coping skills.

Cognitive Behavioral Therapy (CBT). CBT will consist of 6 patient sessions and 3 parent-only sessions with a licensed pain psychologist focused on biopsychosocial model education, goal setting, coping skills training, and cognitive restructuring. The final CBT sessions with the psychologist will focus on relapse prevention, long term goals, reviewing of accomplishments during treatment.

Physical Therapy (PT). PT will consist of 6 sessions with a licensed physical therapist based on Guide to Physical Therapy Practice 3.0⁵¹ consisting of 1) therapeutic exercise, 2) balance and proprioception, 3) strength training, 4) use of modalities (e.g., heat/cold pack).

Discharge will consist of a second biomechanical motion analysis (**[name]**; Motion and Sports Performance Laboratory at SCH), and exit interview, and self-report questionnaires completed by patient and parent.

Follow-up will occur 3 and 6-months post-discharge assessment. During the follow-up period, patients and parents will be asked to complete 7-days of daily diaries and complete self-report questionnaires.

Table 3. Typical Pain Management Sessions

Session	Topic	Adolescent Content	Parent Content
1	Rapport Building, History	Build rapport; obtain patient history. Discuss goals for treatment.	Joint Session: Same content
2	PT Session 1	Adolescent in Physical Therapy	N/A

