5.2 Handling of Study Interventions

The GET Living Intervention will be delivered jointly with a Pain Psychology Therapist (PSY) and Physical Therapist (PT). Sessions will involve both patient and parent.

The Typical Pain Management intervention will be delivered with a Pain Psychology Therapist (PSY) and Physical Therapist (PT) separately. Sessions will involve the patient and 3 parent-only sessions held by the therapist.

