Aim 1 Analysis Plan. GET Living vs. TPM. Linear mixed effects models will be used to compare GET Living to TPM. The outcome of interest for H_{1a} will be FOPQ-C and PFOPOQ total scores. For H_{1b}, outcomes are FDI and ARCS-Protect scores. Exploratory endpoints. Daily Diary (DD): We will use a randomization test (<https://tamalkd.shinyapps.io/scda/>)⁵³ to assess the difference between baseline (BAS) to discharge (END) and BAS to 3 and 6-month follow-up (FU)^{21,54}. We will also examine at what point during treatment significant improvements occur using delayed effect lags (one effect equals 1 day) until p-value 0.05 is reached. Actigraphy: Actilife software will be used to extract data and calculate mean and peak daily activity. Published data reduction methods will be used⁴³. We will model physical activity (mean, peak) at two time points using mixed 2 (time) x 2 (group) ANOVAs. Rate of change in physical activity from BAS to END will also be examined using DD method. Biomechanical assessment: Full body joint kinematic (motion) and kinetic (force) data will be collected with a 20-camera Vicon system (Centennial, CO, USA) with 5 integrated force plates (Bertec; AMTI). Markers will be placed on each participant according to the 3D Plug In Gait model (Vicon) with data recorded and processed in Nexus 2.6.1. Participants will walk, complete the Star excursion balance test and drop jump task^{37,41}. Biomechanical variables (stride length; peak hip and knee extensor moments; peak ankle plantarflexor moment; Star excursion balance score) will be extracted using Event Analyser (Vicon) for error free data reduction. We will model biomechanical variables using mixed 2 (time) x 2 (group) ANOVAs. We will also examine treatment response correlates: age, pain, gender, diagnosis, and readiness to change.

Aim 2: To characterize feasibility of GET Living to inform implementation of a large multi-site RCT.

Hypotheses: GET Living participants will have (1) high treatment satisfaction ratings (mean score ≥ 40 of 60; reflective of satisfied or very satisfied); *Secondary:* (2) $\geq 80\%$ sessions completed on-schedule, $\leq 20\%$ attrition rate, $\geq 80\%$ adolescent and parent daily diary adherence; *Exploratory:* (3) fewer health care costs at 3 and 6-month follow-up compared to TPM.

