Aim 2 Analysis Plan. Satisfaction. We will examine mean satisfaction scores. Adherence/Retention. We will examine mean parent and adolescent adherence to daily diary completion, percent of patients who dropout prior to treatment completion, and percent of sessions completed on-schedule. Health care costs. We will examine mean costs across arms at 3 and 6-month follow-up.

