9.5.5 Feasibility Measures

Feasibility will be measured in terms of treatment satisfaction, acceptability, adherence, fidelity, and healthcare use/cost. Treatment satisfaction will be evaluated by mean satisfaction of the Pain Service Satisfaction Test (PSST)⁶⁰ scores completed by child participants in both intervention groups. Treatment Acceptability will be measured by the Treatment Expectancy and Creditability measure (TEC-C, TEC-P)⁶¹, along with exit interviews collected at the discharge session. Adherence and Retention will be examined through mean parent and patient adherence to daily diary completion, percent of patient who drop out prior to treatment completion, and percent of sessions completed on schedule. A trained research assistant will listen to audio/video recordings of treatment sessions and complete treatment fidelity checklists for content and process, for both parents and child sessions (See Supplemental Materials I for checklists). Healthcare use/cost will be measured at the Baseline and 3 and 6-month follow-up time points with the Healthcare Cost Diary⁶².

Table 6. Assessment Measures

Outcomes & Correlates	Questionnaires & Tests	DD	Full version
Aim 1			
Primary Outcome			
Pain-related Fear Avoidance	Fear of Pain Questionnaire (FOPQ-C; PFOPQ) FOPQ-C: low [0-34] moderate [35-49] high [50-96]; Photographs of Daily Activities for Youth English (PHODA-YE)	x	BAS, END, FU3, FU6
Secondary Outcome			
Functional Disability	Functional Disability Inventory (FDI) mild [0-12] moderate [13-29] severe [30-60]	x	BAS, END, FU3, FU6
Additional Outcomes			
Protective Behaviors	Adult Responses to Child's Symptoms (ARCS), Helping for Health Inventory (HHI)	x	BAS, END, FU3, FU6
Parent Flexibility	Parent Psychological Flexibility Questionnaire (PPFQ-10)	x	BAS, END, FU3, FU6
Pain Acceptance	Chronic pain acceptance questionnaire (CPAQ-A; PPAQ)	x	BAS, END, FU3, FU6
School Functioning	Pediatric Quality of Life – School Functioning Subscale (PedsQL)		BAS, END, FU3, FU6
Exploratory Outcomes			
Biomechanics	Gait (stride length, velocity), vertical drop landing, dynamic postural control		BAS, END
Physical Activity	Daily mean and peak activity via Actigraphy	x	

Correlates			
Pain Severity	Numerical Rating Scale (NRS)	x	BAS, END, FU3, FU6
Pain Catastrophizing	Pain Catastrophizing Scale (PCS-C, PCS-P)		BAS, END, FU3, FU6
Medical History	Pain Questionnaire: Time since onset, previous treatments (Pain-C, Pain-P)		BAS

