Demographics	Age, sex, socioeconomic status (Caregiver History)		BAS
Readiness to change	Pain Stages of Change Questionnaire (PSOCQ-A; PSOCQ-P)		BAS, END, FU3, FU6
Depression	Children's Depression Inventory-2 (CDI-2)		BAS, END, FU3, FU6
Anxiety	Multidimensional Anxiety Scale for Children (MASC)		BAS, END, FU3, FU6
Feasibility Measures			
Treatment Acceptability	Treatment satisfaction (PPST); mean score 40 of 60; satisfied to very satisfied		END, FU3, FU6
Treatment Acceptability	Treatment Expectancy & Credibility (TEC-C; TEC-P);		S1
Treatment Acceptability	% drop-out; Exit Interview (patient/parent feedback)		END
Treatment Adherence	% adherence to daily diary, at-home tasks, sessions completed on-schedule		END
Treatment Fidelity	Process (e.g., reflective listening), Content (session outline adherence)		**
Healthcare Use/Cost	Cost diary		BAS, WK, FU3, FU6

**To be assessed by ongoing coding of audio/video recordings of treatment sessions

BAS=Baseline, DD=Item Generation for Daily Diary; WK= Weekly during treatment, END=End of treatment, FU3=3-month follow-up, FU6=6 month follow-up, S=Session.

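### The exploratory cost comparison covers only the 3- and 6-month follow-up, so it cannot show whether GET Living costs less overall once treatment delivery is counted

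*Combined protocol and SAP*

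**What the plan says.** The Aim 2 cost hypothesis (sections 1.1 and 9.1) is labelled exploratory and predicts, for GET Living, "fewer health care costs at 3 and 6-month follow-up compared to TPM". The analysis is a single sentence: "We will examine mean costs across arms at 3 and 6-month follow-up". No test, interval, baseline adjustment or unit cost is given, and no section plans to cost the delivery of either treatment.

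The documents disagree on when cost data are collected. The text of section 9.5.5 states: "Healthcare use/cost will be measured at the Baseline and 3 and 6-month follow-up time points with the Healthcare Cost Diary". Table 6, in the same section, lists the cost diary at baseline, WK, FU3 and FU6, and its legend defines "WK= Weekly during treatment".

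On staffing, the Précis describes "1-hour sessions of GET Living for 12 sessions jointly facilitated by a pain psychology therapist and physical therapist", and section 5.1 says GET Living patients "will participate in 12 sessions, 1-hour each, delivered twice a week over for up to 6 weeks". Section 3 (Treatment Conditions) instead gives 50-minute sessions. It also explains that, in exposure sessions that are not co-led, the physical therapist works with the adolescent while the psychologist sees the parent, so both are occupied. In TPM the two providers work separately (section 5.2). Section 5.1 says: "CBT will consist of 6 patient sessions and 3 parent-only sessions with a licensed pain psychologist". It adds 6 physical therapy sessions.

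**The concern.** The two treatments differ in staffing by design, and that difference falls wholly before the window that the cost analysis looks at. A lower mean cost at 3 and 6 months is therefore compatible with a higher total cost from the start of treatment.

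This matters because Aim 2 is meant to inform a multi-site trial, and section 2.1 looks ahead to nationwide use. For either purpose, the cost of delivering the treatment is part of the question. The risk of misreading is increased by the statement in sections 3 and 5.1 that TPM was enlarged to equalise dose. A reader could take that to mean the arms cost about the same to deliver, although provider time differs.

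Separately, families may be completing weekly cost diaries that no analysis uses. Or staff who follow the text of section 9.5.5 may not collect them at all.

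**Working it through.** The documents state no provider-hour total and no cost figure, so there is nothing of the plan's own to reproduce. The check builds provider time from the session descriptions.

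**Formula.** Provider-hours per patient = sessions × hours per session × providers occupied.

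**GET Living, 12 sessions, two providers**
- 1-hour sessions (Précis, section 5.1): 12 × 1 × 2 = 24 hours, that is 12 psychology and 12 physical therapy.
- 50-minute sessions (section 3): 12 × 50/60 × 2 = 20 hours, that is 10 and 10.

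**TPM, one provider per session, 1 hour each (section 5.1)**
- 6 psychology + 3 parent-only + 6 physical therapy = 15 hours, that is 9 psychology and 6 physical therapy. The length of the parent-only sessions is not stated separately; 1 hour is assumed.

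**Difference per patient**
- 24 − 15 = 9 hours (3 psychology, 6 physical therapy), ratio 24/15 = 1.6.
- 20 − 15 = 5 hours (1 psychology, 4 physical therapy), ratio 20/15 = 1.33.
- If TPM sessions were also 50 minutes: 15 × 50/60 = 12.5, and 20 − 12.5 = 7.5 hours, inside the same range.

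**Sensitivity to the number of sessions.** A note in Table 2 allows 3 to 9 exposure sessions, where the table lays out 6 among 12. If that changes the total, GET Living has 12 − 3 = 9 to 12 + 3 = 15 sessions:
- 9 sessions: 9 × 50/60 × 2 = 15 hours, or 9 × 1 × 2 = 18.
- 15 sessions: 15 × 50/60 × 2 = 25 hours, or 15 × 1 × 2 = 30.

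Set against 15 hours for TPM, GET Living uses more provider time in every combination except 9 sessions of 50 minutes, where the two are equal.

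**In money.** No hourly rate is given. At an assumed $100 to $250 for either provider type:
- 5 hours: 5 × $100 = $500 to 5 × $250 = $1,250 per patient.
- 9 hours: 9 × $100 = $900 to 9 × $250 = $2,250 per patient.

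**What the planned comparison can see.** Write D for the extra delivery cost of GET Living and S for its saving during follow-up. If other care during treatment costs the same in both arms, the total difference (GET Living minus TPM) is D − S. The planned analysis estimates only −S. GET Living is cheaper overall only if S exceeds D, here $500 to $2,250 per patient under the assumed rates. The documents give no expected value of S.

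**The case against.** The strongest reply is that the analysis does what the hypothesis asks. The hypothesis is exploratory and names the 3- and 6-month follow-up, the analysis only describes means, and no section makes cost a criterion for going on to the larger trial. The numerical Aim 2 targets concern satisfaction, sessions on schedule, attrition and diary adherence. The window of a cost analysis is a legitimate choice. All of this stands, and it is why the point concerns what the result can be used for and is not a claim that hypothesis and analysis disagree.

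Three stronger readings are tempting, and the documents do not support them:
- A reader might infer that GET Living costs more overall. That would need unit costs, the follow-up saving and other treatment-period costs, none of which is given.
- A reader might infer that the plan sets out to claim lower health care costs without limit of time. The hypothesis carries its time qualifier in both sections 1.1 and 9.1.
- A reader might infer that no treatment-period cost data will exist. Table 6 schedules a weekly diary, although the documents do not say whether it records study-delivered sessions.

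It is also fair to say that anyone can work out the staffing gap from the session tables, and that TPM here exceeds the historical average of 5 psychology and 4 physical therapy sessions (section 5.1). A trial-based total would therefore not be a usual-care cost. These points limit how far a total can be generalised. They do not make the follow-up-only mean a substitute for it.

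**Conclusion.** The point holds as a limit on an exploratory analysis. The planned comparison cannot show whether GET Living costs less overall, because it omits a treatment period in which GET Living, at the planned 12 sessions, takes about 20 to 24 provider-hours per patient against about 15. The gap of 5 to 9 hours rests on both GET Living providers being occupied throughout and on 1-hour parent-only TPM sessions. It assumes full attendance, and it may shift if the number of exposure sessions changes the total. The corresponding $500 to $2,250 per patient rests in addition on an assumed hourly rate.

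Two further defects do not depend on those assumptions. Baseline cost is collected and not used, and section 9.5.5 contradicts Table 6 on the weekly diary, which no analysis uses under either schedule.

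**What to change.** In the Aim 2 Analysis Plan and section 9.5.5:

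1. Adjust the between-arm cost comparison for the baseline cost diary.
2. Keep the follow-up-only cost. Beside it, report total cost per randomised patient from start of treatment to 6 months, with a confidence interval. The total is provider time from session records at a stated unit cost per provider type, plus weekly diary costs, plus the 3- and 6-month diaries. Study sessions must not be counted twice if families also enter them in the diary.
3. Reconcile the text of section 9.5.5 with Table 6 on the weekly diary. Reconcile the GET Living session length between the Précis, section 3 and section 5.1.
4. State that any follow-up-only result concerns costs after treatment and excludes the cost of the study treatment.

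The cost is protocol and SAP wording and a modest amount of analysis. Section 10.1 already has session documentation collected weekly, but no section says that provider minutes are logged, so provider time may have to be taken as scheduled for each session attended. The total also needs a stated rule for missing diaries, since section 9.2 expects 58 of 74 patients at the end of follow-up (74 − 58 = 16 without complete data). The cost result may look less favourable to GET Living.

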9.2 Sample Size and Randomization

We chose the largest feasible study size to obtain as precise estimates as possible of improvement in adolescent disability while ensuring adequate power for the treatment difference in the improvement in adolescent pain-related fear. This gave us a starting total sample size of 74 (37 in each arm). Based on pilot data, we expect roughly 19% attrition during treatment to a total of 60 and further attrition to 58 at end of follow-up.

Power calculations were first performed using the simplified approach of paired t-tests for the change from baseline to 3 and 6-months on those with 3 and 6-months data. For this approach, we used means and standard deviations of observed changes in pilot data. We then simulated data from our analytic model using the standard deviations at each time point and standard deviations of change to calculate correlation and hence the random effect and error variances. The mixed models simulation allowed us to use more data and yielded slightly higher power estimates.

Primary Outcome: In our primary power calculation, we assumed that the improvement in adolescent pain-related fear at 3 and 6-months would be 22.4 in GET Living and 5 in TPM, a difference of 17.4, with a standard deviation for change of 21. Under this scenario we will have power of 87% with 58 (29 in each arm) at end of study. Under more conservative assumptions, we still have power of 80% with only 52 at the end of study and a treatment difference of 16.6. With a smaller standard deviation of 18.9, we will have power of 80% with 50 at end of study and a treatment difference of 15.4.

Other Outcomes: For parent pain-related fear, our estimated treatment difference at 3 and 6-months is 13 with an estimated standard deviation for change of 8.5. This would give us power close to 100% for 58 at end of study and we would still have 90% power with a treatment difference of only 8 and only 50 left at end of study.

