For adolescent disability, our estimated treatment effect at 3 and 6-months is 7 with a standard deviation for change of 11.2, yielding power based on the t-test of 65% assuming 58 at end of study. We also created 5000 simulated datasets using a mixed effects model with standard deviations of 11.2 for change and 12.6 at each time point and estimated power by the fraction of simulated datasets in which the treatment difference at 3 and 6-months was significant at level 0.05. This provided a slightly higher power estimate of 67% and an estimated power of 79% if the treatment difference is 8 (1 point larger than expected).

Treatment Assignment Procedures

After a 2-week pre-treatment baseline period, patients will be randomized to either GET Living or TPM and stratified on fear and disability scores (see **Table 6** for scoring criteria). A block

randomization strategy will be used with randomly generated blocks of 2 and 4 to assure near equal distributions across arms and minimize the probability of predicting the next assignment. A randomization spreadsheet with four strata will be created by the study biostatistician, [name] (please see **Table 5** in section 6.2.2 for fear and disability stratification).

Patients will be randomized by an un-blinded research coordinator or postdoctoral fellow. Those who are randomized to the TPM group can opt to participate in GET Living after their study assessments are complete (6.5 months after baseline). They will no longer be considered a participant of this study at that time.

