9.6 Data Analyses

Our statistician, [name], will conduct analyses. Linear mixed effects models will be used for Aim 1. We chose the largest feasible study size to obtain as precise estimates as possible of treatment difference in our primary outcome, adolescent pain-related fear. With a starting sample of 74 (37/37), we expect 58 at follow-up (18% discharge attrition, 5% at 3 and 6-month follow-up). Using GET Living pilot data (see Table 2), we used a mixed model simulation using the standard deviations at each time point and standard deviations of change to calculate correlation and hence the random effect and error variances. In our primary power calculation, we assumed that the improvement in adolescent pain-related fear at 3 and 6-months would be 22.4 in GET Living and 5 in TPM¹⁹, a difference of 17.4, with a standard deviation for change of 21. Under this scenario we will have 87% power with 58 (29 in each arm) at study end. Under more conservative assumptions, we still have power of 80% with only 52 at the end of study and a treatment difference

of 16.6. With a smaller standard deviation of 18.9, we will have power of 80% with 50 at end of study and a treatment difference of 15.4.

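### The exploratory cost comparison states no baseline adjustment and no confidence interval, although the cost diary is completed at baseline, so it is less precise than it could be

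*Combined protocol and SAP*

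**What the plan says.** The cost hypothesis is comparative and directional. Section 1.1 and the Aim 2 text in Section 9.1 both list, as exploratory, "fewer health care costs at 3 and 6-month follow-up compared to TPM". The analysis is one sentence in the Aim 2 Analysis Plan: "We will examine mean costs across arms at 3 and 6-month follow-up".

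A baseline value is collected. Section 9.5.5 states: "Healthcare use/cost will be measured at the Baseline and 3 and 6-month follow-up time points with the Healthcare Cost Diary". Table 6 also lists the cost diary at baseline, weekly during treatment, and at both follow-ups. No section gives the baseline value a use.

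No other section fills the gap. Section 9.6 says "Linear mixed effects models will be used for Aim 1", and the outcomes named for those models in Section 9.1 are the two fear scores, disability and protective parent responses. Cost belongs to Aim 2. Allocation is "stratified on fear and disability scores" (Section 9.2), so prior health care use is not a stratification factor.

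**The concern.** Past use of care usually says something about later use, and a few heavy users can move an arm mean in a trial of this size. If one arm happens to start with more of them, its follow-up mean will tend to be higher whatever the treatment does. The baseline diary is the obvious means of taking that part out, and the stated analysis does not mention it.

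The plan handles its other exploratory comparisons differently. In Section 9.1 the daily diaries are assessed against the baseline period, and actigraphy and biomechanics are modelled with time and group, so baseline enters each of them.

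At stake is how far the cost statement can be relied on. Aim 2 is meant to inform a larger multi-site trial, and two arm means without an interval show neither the uncertainty nor any starting imbalance.

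**Working it through.** **Sample size.** Section 9.2 says "we expect roughly 19% attrition during treatment to a total of 60 and further attrition to 58 at end of follow-up", and 74 × 0.81 = 59.9 agrees. It continues: "Under this scenario we will have power of 87% with 58 (29 in each arm) at end of study". That power is for adolescent fear, with a difference of 17.4 and an SD of change of 21. The standard error is 21 × √(2/29) = 5.51 and 17.4 / 5.51 = 3.16. A two-sided 5% two-sample t-test then has 87.3% power, so the stated 87% reproduces and 29 per arm is the right figure to use. The documents state no power, SD or expected difference for cost.

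**Size of a chance baseline imbalance.** In units of the cost SD, the standard error of the difference between two arm means at baseline is √(2/29) = 0.263, so the 95% range is ±1.96 × 0.263 = ±0.51 SD. On a normal approximation, the chance of an imbalance above 0.25 SD in either direction is 34%, and above 0.5 SD it is 5.7%. If the coefficient of variation of cost is 1 to 2 (an assumption), one standard error is 26% to 53% of mean cost.

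**Effect on the follow-up comparison.** Let r be the correlation between baseline and follow-up cost, with equal SDs at both times. Given a baseline imbalance b, the expected follow-up difference under no treatment effect is r × b. Relative to raw follow-up means, the standard error is multiplied by √(1 − r²) with covariate adjustment and by √(2(1 − r)) with a change score. The range of r is an assumption.

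| r | Shift from a one-SE imbalance (r × 0.263 SD) | SE multiplier, adjusted | Cut in SE | SE multiplier, change score |
|---|---|---|---|---|
| 0.3 | 0.08 SD | 0.95 | 5% | 1.18 |
| 0.5 | 0.13 SD | 0.87 | 13% | 1.00 |
| 0.6 | 0.16 SD | 0.80 | 20% | 0.89 |
| 0.7 | 0.18 SD | 0.71 | 29% | 0.77 |

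The equivalent gain in sample size, 1/(1 − r²), is 1.10, 1.33, 1.56 and 1.96 times. The change score is less precise than raw means whenever r is below 0.5.

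**Illustration.** The plan states no test for cost. If a two-sided 5% test were applied to a true difference of 0.5 SD with 29 per arm, power would be 48% on raw means. With adjustment it would be 51%, 59%, 66% and 76% for the four values of r. At r = 0.5, the raw test would have 70% power if a one-SE imbalance favoured GET Living and 26% if it went against it.

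**The case against.** The case for leaving the sentence alone has real weight.

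- **Randomisation already covers this.** The raw difference is unbiased over repeated randomisations, and its standard error already contains chance baseline imbalance. The shift of r × b is part of ordinary sampling error, not an addition to it. This stands. What remains is avoidable imprecision, and the dependence of this one trial's estimate on the imbalance that occurs. Strictly, the guarantee applies to everyone randomised. About 58 of 74 are expected at the end of follow-up, so balance among those analysed is a little less secure.
- **Adjustment is not excluded.** The plan neither states nor rules it out, so the most that can be said is that none is stated. Even so, silence leaves the choice open until the data are seen.
- **The endpoint is exploratory.** It carries no success threshold, unlike satisfaction, attrition and diary adherence. This stands, and it limits the importance of the point.
- **Stratification may help.** The Précis and Section 2.1 link pain-related fear to continued heavy use of care, so stratifying on fear and disability may balance cost in part. No figure is given. To that extent 0.26 SD is an upper value.

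A reader might infer that the cost result would mainly show which arm drew the heavy users. The arithmetic does not support that. The share of follow-up variance explained by baseline is r², which is 9% at r = 0.3, 25% to 36% at r of 0.5 to 0.6, and 49% at 0.7. More than half of the chance variation is unrelated to baseline cost throughout this range.

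**Conclusion.** The point holds as a modest improvement in precision to an exploratory comparison. The plan collects a baseline cost value, states a between-arm cost hypothesis, and describes an analysis with no stated use of that value and no interval. Under the assumption that r lies between 0.3 and 0.7, adjustment cuts the standard error by about 5% to 29%, and by 13% to 20% at r of 0.5 to 0.6.

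The size rests on quantities the documents do not give: the cost SD, its skewness and r. The baseline diary's recall period is not stated either, so a low r cannot be ruled out, and at r = 0.3 the gain is small. The formula √(1 − r²) is for a linear model and ignores the few degrees of freedom spent on covariates.

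The documents do not support reading this as bias in the cost comparison, or as a threat to the fear and disability conclusions, which have their own models.

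**What to change.** In the Aim 2 Analysis Plan (Section 9.1), replace the cost sentence with a between-arm difference in mean follow-up cost, estimated from a linear model adjusted for baseline diary cost and the two stratification factors (fear and disability). Give a bootstrap 95% confidence interval, because costs are likely to be skewed, and label the result exploratory. State whether 3 and 6 months are analysed separately or as a total.

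Use covariate adjustment, not a change score, for the reason shown in the table. A gamma model with log link is a less convenient choice: it cannot take patients with zero cost directly, and it yields a ratio that must be converted to a difference in means.

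Also state the recall period of the baseline diary so that it is comparable with follow-up, and align Section 9.5.5 with Table 6, which alone lists weekly cost diaries during treatment.

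The cost is a change of wording and slightly more analysis work, with no new data. If r turns out to be low, the gain will be slight.
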